18.1 Important Protocol Deviations

Protocol reference text	Category of Protocol Deviation	Description of Protocol Deviations	Deviation Code	Protocol Deviation Category	Protocol Section	Proposed check/comment
Inclusion criteria: For the subject to be eligible for inclusion, each criterion must be checked 'YES':						
Criterion1: Signed written informed consent.	Eligibility and Entry Criteria	Subject did not meet inclusion criterion 1 (signed informed consent form).	PDEV01	Important	Section 5.3.1	If date of written informed consent(I_ICDT) = missing. Or date of written informed consent (I_ICDT) > Start date of First Avelumab administration (I_EXSTDTM). Medical Review Required.
Criterion 4: Histologically or cytologically proven locally advanced unresectable or metastatic solid tumor, for which no standard therapy exists or standard therapy has failed.	Eligibility and Entry Criteria	Subject did not meet inclusion criterion 4 (histologically or cytologically proven metastatic or locally advanced solid tumor).	PDEV02	Important	Section 5.3.1	Medical review required.
Exclusion criteria: For the subject to be eligible for inclusion, each criterion must be checked 'NO':						
Criterion 1: Prior therapy with any antibody/drug targeting T cell coregulatory proteins (immune checkpoints) such as PD-1, PD-L1, cytotoxic T-lymphocyte antigen-4 (CTLA-4), 4-1BB, LAG-3, TIM-3 or anti-CD127.	Eligibility and Entry Criteria	Subject met exclusion criterion 1	PDEV03	Important	Section 5.3.2	Medical Review required.

Criterion 2: Concurrent anticancer treatment(s) (e.g., cytoreductive therapy, radiotherapy [with the exception of *palliative bone-directed radiotherapy and radiotherapy administered to superficial lesions], immune therapy, or cytokine therapy except for erythropoietin). Radiation to more than 30% of the bone marrow or with a wide field of radiation should not be used within 28 days prior to the first administration of avelumab and is prohibited throughout the study	Eligibility and Entry Criteria	Subject met exclusion criterion 2	PDEV04	Important	Section 5.3.2	Medical Review required.
Criterion 18: Clinically significant (that is, active) cardiovascular disease: cerebral vascular accident/stroke (< 6 months prior to enrolment), myocardial infarction (< 6 months prior to enrolment), unstable angina pectoris, congestive heart failure (New York Heart Association Classification Class \geq II), or serious cardiac arrhythmia requiring medication (including corrected QT interval prolongation of > 470 msec calculated according to Fridericia and/or pacemaker or prior diagnosis of congenital long QT syndrome)	Eligibility and Entry Criteria	Subject met exclusion criterion 18	PDEV05	Important	Section 5.3.2	Medical Review required.
Subjects that develop withdrawal criteria whilst on the study but are not withdrawn	Other criteria	Subject developed Significant clinical deterioration, but continued on the study	PDEV06	Important	Section 5.5.2	Medical review required/ Programmatically checked.
Subjects that develop withdrawal criteria whilst on the study but are not withdrawn	Other criteria	Subject developed Grade \geq 4 ADRs, but continued on the study	PDEV07	Important	Section 5.5.2	Medical review required/ Programmatically checked.
Subjects that develop withdrawal criteria whilst on the study but are not withdrawn	Other criteria	Subject developed AE resulting in the discontinuation of avelumab being desired or considered necessary by the Investigator and/or the subject, but	PDEV08	Important	Section 5.5.2	Medical review required.

		continued on the study				
Subjects that develop withdrawal criteria whilst on the study but are not withdrawn	Other criteria	Subject became pregnant, but continued on the study.	PDEV09	Important	Section 5.5.2	Medical review required/ Programmatically check
Non-permitted concomitant medication during the study	Concomitant Medication Criteria	Subject took prohibited medication during the study.	PDEV10	Important	Section 6.5.2	Medical Review/ Programmatically check
Subjects overdosed ($\geq 120\%$ of assigned dose)	IP Compliance	Subject was overdosed.	PDEV11	Important	Section 6.12	Programmatically check with administration page Actual dose (I_EXADOSE) $\geq 120\%$ of 20mg/kg.

18.2 Description of the Case Definition for Assessment of Immune-Related AEs and IRRs

Immune-Related Adverse Events

Immune-related adverse events (irAEs) will be identified programmatically. AEs which satisfy all of the following criteria will be flagged as immune-related:

- 1) The AE preferred term matches a preferred term on the list of pre-selected MedDRA terms.
- 2) The AE onset occurs after the first study drug administration and no more than 90 days after last dose.
- 3) On the AE details eCRF page [aedt], the question “Were Corticosteroids, Immunosuppressants, or hormonal therapy (e.g. Thyroid, insulin) applied?” has the answer “Yes” selected.
- 4) On the irAE specific eCRF page [irae], either:
 - a. The question “Does any of the following provide a clear etiology for the event?” has the answer “No” selected, indicating that the AE is not attributable to underlying cancer disease/PD, prior or concomitant medications/procedures, nor another medical condition such as an infection, pre-existing disease or investigator’s choice of alternative etiology other than irAE.

OR

- b. The irAE specific eCRF indicates that a biopsy was performed and the question “Is the histopathology/biopsy consistent with an immune-related event?” has the answer “Yes” selected.

In the case that criteria (1) through (3) are met, and entries for condition (4) are missing, the following rules will be applied:

- If the answer to “Does any of the following provide a clear etiology for the event?” (4a) is missing, the event will be considered as irAE (irrespective of biopsy results).
- If the answer to “Is the histopathology/biopsy consistent with an immune-mediated event?” (4b) is missing, or if no biopsy was performed, and condition (4a) is not satisfied (i.e. “Yes” is selected as the answer to the question “Does any of the following provide a clear etiology for the event?”), the event will be considered as a non-irAE.

Infusion Related Reactions

Infusion related reactions are identified based on a list of MedDRA PTs and criteria on the timely relationship according to table below:

Criteria for infusion related reactions

Infusion related reactions	
Reactions - Considered when onset is on the day of study drug infusion (during or after the infusion) or the day after the study drug infusion (irrespective of resolution date):
 
• Infusion related reaction• Drug hypersensitivity• Anaphylactic reaction• Hypersensitivity• Type 1 hypersensitivity 
Signs and Symptoms - occurring on the day of study drug infusion (during or after the infusion) and resolved with end date within 2 days after onset
 
• Pyrexia• Chills• Flushing• Hypotension• Dyspnoea• Wheezing• Back pain• Abdominal pain• Urticaria
----------------------------	--

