#### 3.3.1 Rationale for 10 mg/kg Once Weekly Dose-Escalation Cohort

Avelumab dosing regimen of 10 mg/kg once weekly for the first 12 weeks followed by once every 2 weeks starting at Week 13 would be evaluated with the following considerations:

- An exposure-efficacy response relationship was observed in second-line NSCLC subjects treated with 10 mg/kg once every 2 weeks. In 184 avelumab-treated subjects, unselected for PD-L1 expression, ORRs were 8.7%, 10.9%, 19.6%, and 17.4% for increasing quartiles of trough concentrations after first dose ( $C_{\text{troughfirst-dose}}$  Q1-4). Using  $\geq 1\%$ ,  $\geq 5\%$ ,  $\geq 50\%$ , and  $\geq 80\%$  PD-L1 staining cutoffs, subjects in the upper half of exposure ( $C_{\text{troughfirst-dose}}$  Q3-4 [n = 92]), had ORRs of 25% (n = 59), 26% (n = 39), 33% (n = 21), and 43% (n = 14),

respectively (data on file). The trends of longer progression-free survival (PFS) and OS for subjects in the higher exposure quartiles based on steady state trough concentration was also seen in the cohorts of urothelial cancer, gastric cancer, and others.

- Population PK analysis and simulation showed that a 10 mg/kg once every week regimen will increase the exposure, the median steady state trough concentration is predicted to increase from 22.9 µg/mL (range: 4.2-74.5 µg/mL) in the once every 2 weeks regimen to 83.3 µg/mL (range: 28.6-204 µg/mL) in the once weekly regimen (data on file), potentially enhancing efficacy as suggested by the exposure-efficacy analyses described above.
- In the above second-line NSCLC cohort, higher avelumab exposure was associated with a modest increase in immune-related AEs (irAEs). For all other AEs analyzed, AE incidence appeared to not increase with increasing exposure. And based on population PK modeling, median exposures are not expected to exceed those for previously administered regimens; the steady state maximum concentration is similar to that for 10 mg/kg once every 2 weeks regimen, while steady state AUC is similar to that for 20 mg/kg once every 2 weeks regimen (data on file).

In summary, the dosing regimen of 10 mg/kg once a week for 12 weeks followed by 10 mg/kg once every 2 weeks starting at Week 13 is supported by the exposure-efficacy relationship, time-to-response analyses, and an acceptable benefit-risk profile, as described above.

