**Table 6-2 Management of Immune-related Adverse Events**

Gastrointestinal irAEs		
Severity of Diarrhea/Colitis (NCI-CTCAE v4.03)	Initial Management	Follow-up Management
Grade 1 Diarrhea: < 4 stools/day over baseline Colitis: asymptomatic	Continue avelumab therapy Symptomatic treatment (eg, loperamide)	Close monitoring for worsening symptoms Educate subject to report worsening immediately If worsens: treat as Grade 2, 3, or 4
Grade 2 Diarrhea: 4 to 6 stools per day over baseline; iv fluids indicated < 24 hours; not interfering with activities of daily living Colitis: abdominal pain; blood in stool	Withhold avelumab therapy Symptomatic treatment	If improves to Grade ≤ 1: resume avelumab therapy If persists > 5 to 7 days or recurs: treat as Grade 3 to 4
Grade 3 to 4 Diarrhea (Grade 3): ≥ 7 stools per day over baseline; incontinence; iv fluids ≥ 24 hours; interfering with activities of daily living Colitis (Grade 3): severe abdominal pain, medical intervention indicated, peritoneal signs Grade 4: life-threatening, perforation	Withhold avelumab for Grade 3 Permanently discontinue avelumab for Grade 4 or recurrent Grade 3 1.0 to 2.0 mg/kg/day prednisone iv or equivalent Add prophylactic antibiotics for opportunistic infections Consider lower endoscopy	If improves: Continue steroids until Grade ≤ 1, then taper over at least 1 month, resume avelumab therapy following steroids taper (for initial Grade 3) If worsens, persists > 3 to 5 days or recurs after improvement: add infliximab 5 mg/kg (if no contraindication) Note: infliximab should not be used in cases of perforation or sepsis
Dermatological irAEs		
Grade of Rash (NCI-CTCAE v4.03)	Initial Management	Follow-up Management
Grade 1 to 2 Covering ≤ 30% body surface area	Continue avelumab therapy Symptomatic therapy (eg, antihistamines, topical steroids)	If persists > 1 to 2 weeks or recurs: Withhold avelumab therapy Consider skin biopsy  Consider 0.5 to 1.0 mg/kg/day prednisone or equivalent Once improving, taper steroids over at least 1 month, consider prophylactic antibiotics for opportunistic infections, and resume avelumab therapy following steroids taper If worsens: treat as Grade 3 to 4

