Grade 2 AST or ALT > 3.0 to ≤ 5 × ULN and/or total bilirubin > 1.5 to ≤ 3 × ULN	Withhold avelumab therapy Increase frequency of monitoring to every 3 days	If returns to Grade ≤ 1: Resume routine monitoring; resume avelumab therapy If elevation persists > 5 to 7 days or worsens: Treat as Grade 3 to 4
Grade 3 to 4 AST or ALT > 5 × ULN and /or total bilirubin > 3 × ULN	Permanently discontinue avelumab therapy Increase frequency of monitoring to every 1 to 2 days 1.0 to 2.0 mg/kg/day prednisone or equivalent Add prophylactic antibiotics for opportunistic infections Consult gastroenterologist/hepatologist Consider obtaining MRI/CT scan of liver and liver biopsy if clinically warranted	If returns to Grade ≤ 1: taper steroids over at least 1 month If does not improve in > 3 to 5 days, worsens or rebounds: add mycophenolate mofetil 1 g twice daily If no response within an additional 3 to 5 days, consider other immunosuppressants per local guidelines
Renal irAEs		
Grade of Creatinine Increased (NCI-CTCAE v4.03)	Initial Management	Follow-up Management
Grade 1 Creatinine increased > ULN to 1.5 × ULN	Continue avelumab therapy	Continue renal function monitoring If worsens: Treat as Grade 2 to 3 or 4
Grade 2 to 3 Creatinine increased > 1.5 and ≤ 6 × ULN	Withhold avelumab therapy Increase frequency of monitoring to every 3 days 1.0 to 2.0 mg/kg/day prednisone or equivalent. Add prophylactic antibiotics for opportunistic infections Consider renal biopsy	If returns to Grade ≤ 1: Taper steroids over at least 1 month, and resume avelumab therapy following steroids taper. If worsens: Treat as Grade 4.
Grade 4 Creatinine increased > 6 × ULN	Permanently discontinue avelumab therapy Monitor creatinine daily 1.0 to 2.0 mg/kg/day prednisone or equivalent. Add prophylactic antibiotics for opportunistic infections Consider renal biopsy Nephrology consult	If returns to Grade ≤ 1: Taper steroids over at least 1 month
Cardiac irAEs		
Myocarditis	Initial Management	Follow-up Management

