15.2.5 Adverse Events of Special Interest

Any AE that is suspected to be a potential irAE and infusion related reactions will be considered an adverse event of special interest (AESI). The frequency (number and percentage) of patients with each of the following will be presented for treatment emergent irAEs, by dose level/cohort:

- Any irAEs

- Any related irAEs
- Any serious irAEs
- Any related serious irAEs
- Any irAEs by NCI-CTCAE severity grade (≥ 3 , ≥ 4)
- Trial treatment related irAEs by NCI-CTCAE severity grade (≥ 3 , ≥ 4)
- Any irAEs leading to treatment discontinuation
- Any related irAEs leading to treatment discontinuation
- Any irAEs leading to death
- Any related irAEs leading to death

The frequency (number and percentage) of patients with each of the following will be presented for treatment emergent IRRs, by treatment cohort:

- Any IRRs
- Any related IRRs
- Any serious IRRs
- Any related serious IRRs
- Any IRRs by NCI-CTCAE severity grade (≥ 3 , ≥ 4)
- Trial treatment related IRRs by NCI-CTCAE severity grade (≥ 3 , ≥ 4)
- Any IRRs leading to treatment discontinuation
- Any related IRRs leading to treatment discontinuation
- Any IRRs leading to death
- Any related IRRs leading to death

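### The SAP flags an AE as immune-related only if corticosteroids, immunosuppressants or hormones were given, so irAEs that Protocol Table 6-2 manages without them cannot reach the irAE rows

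*SAP*

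**What the plan says.** SAP 18.2 identifies irAEs by program: "AEs which satisfy all of the following criteria will be flagged as immune-related". The criteria are (1) a preferred term on a pre-selected list, (2) onset after the first dose and no more than 90 days after the last, (3) a Yes to "Were Corticosteroids, Immunosuppressants, or hormonal therapy (e.g. Thyroid, insulin) applied", and (4) either no clear other etiology (4a) or a Yes to "Is the histopathology/biopsy consistent with an immune-related event" (4b). The rules for missing answers begin "In the case that criteria (1) through (3) are met, and entries for condition (4) are missing", so they concern criterion 4 alone.

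SAP 15.2 refers to this case definition. It feeds the two irAE lines of the TEAE overview in SAP 15.2.1, the ten irAE lines of SAP 15.2.5 and the irAE flag in the listing of immunogenicity data with AEs in SAP 16.3.

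SAP 15.2.5 opens with a wider idea: "Any AE that is suspected to be a potential irAE and infusion related reactions will be considered an adverse event of special interest". Protocol 7.4.1.1 uses the same definition. Neither sets a treatment condition.

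Protocol Table 6-2 gives the initial management of Grade 2 diarrhea/colitis as "Withhold avelumab therapy Symptomatic treatment", and of Grade 2 liver test elevation as "Withhold avelumab therapy Increase frequency of monitoring to every 3 days".

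**The concern.** The label and the content of the irAE rows do not match. A row headed as any irAE would hold only irAEs that were treated with one of three drug classes, while the protocol both defines the event by suspicion and manages some irAEs without those drugs. Protocol 6.5.5.2 lets the site treat a Grade 1 to 2 irAE either symptomatically or with moderate-dose steroids. Two subjects with the same event could therefore be classified differently because of the treatment chosen.

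This matters because Protocol 3.4 names irAEs as one of two primary identified risks. In the rationale for the once-weekly cohort, Protocol 3.3.1 reports that in an earlier lung cancer cohort "higher avelumab exposure was associated with a modest increase in immune-related AEs". The weekly cohort has no DLT assessment (Protocol 5.1.1.1), so its safety is read mainly from the AE tables by cohort. An undercount of low- and moderate-grade irAEs would fall in those tables.

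**Working it through.** The plan gives no figure to reproduce. The check applies the SAP rule to the protocol's own management table.

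**Step 1: the rule.** From SAP 18.2, flag = C1 AND C2 AND C3 AND (4a OR 4b). Put C3 = No and the flag is No, whatever C1, C2, 4a and 4b say. A biopsy consistent with an immune-related event is an alternative to 4a and does not replace C3. The missing-data rules start only after criteria 1 to 3 are met, so they cannot restore the event. No rule is given for a missing answer to C3.

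**Step 2: the rows of Table 6-2 whose initial management includes no corticosteroid, immunosuppressant or hormone.**

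| Row | Avelumab | Systemic steroid enters the management when | Certain to be an AE? |
|---|---|---|---|
| Diarrhea/colitis G1 | continue | it worsens to G3-4 handling | depends on no laboratory rule |
| Diarrhea/colitis G2 | withhold | it lasts more than 5 to 7 days or recurs | depends on no laboratory rule |
| Pneumonitis G1 | consider withholding | it worsens to G2 or above | no: radiographic change only |
| Liver tests G1 | continue | it worsens to G3-4 handling | no: laboratory finding |
| Liver tests G2 | withhold | it lasts more than 5 to 7 days or worsens | no: laboratory finding |
| Creatinine G1 | continue | it worsens to G2 or above | no: laboratory finding |

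Protocol 6.5.5.2 also has persistent Grade 1 to 2 irAEs managed like high-grade ones, which is a further route to steroids. The last column follows Protocol 7.4.1.1: abnormal laboratory and other investigational findings are AEs only if they are symptomatic, lead to discontinuation or are judged medically important.

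Grade 1 to 2 rash is not counted, because Table 6-2 gives topical steroids as an example. Hyperthyroidism is not counted either, because antithyroid treatment may or may not be recorded as hormonal therapy.

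**Step 3: follow one event.** A subject has Grade 2 diarrhea/colitis, avelumab is withheld, treatment is symptomatic, and the event improves to Grade 1 or less within 5 days. The site has followed Table 6-2 and answers No to criterion 3. By Step 1 the event is not an irAE. It contributes to none of the two irAE lines in SAP 15.2.1 or the ten in SAP 15.2.5.

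**Step 4: effect on one rate.** SAP 15.2.5 counts patients.
- Cohort of 6, one subject whose only irAE is missed: 1/6 = 16.7, about 17 percentage points.
- Same cohort, and the subject has another irAE that is flagged: 0 points in the any-irAE row.
- The 3 mg/kg cohort if it stays at 3 subjects: 1/3 = 33 points for one such subject.

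**The case against.** A treatment-based case definition can be a deliberate choice for specificity. SAP 15.2 calls it a two-level approach, and Protocol 7.4.1.1 presents the suspicion-based definition as one for safety monitoring, so the two may serve different purposes. That stands as a reason to keep the definition. It does not justify using it as the only one under an unrestricted label, directly below a definition based on suspicion.

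Several limits on the concern also stand:
- The preferred-term list is not in the documents. If a term is absent, criterion 1 excludes the event, not criterion 3.
- Four of the six rows in the table above may never produce an AE. Only the two diarrhea/colitis rows are free of that doubt.
- Events that persist or worsen reach steroid treatment and can then qualify. The loss is confined to those that resolve first.
- The events remain in the TEAE tables by preferred term and grade, in the related tables where judged related, and in the AE listings. Gradable liver and creatinine shifts are tabulated whether or not an AE was reported. With about 21 to 24 subjects, individual cases can be read, although nothing marks them as immune-related.
- The irAE flag enters neither the DLT definition nor the escalation rules.

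A reader might count 6 of the 14 graded rows for gut, skin, lung, liver and kidney and infer that about 43% of irAEs are lost. The documents do not support that. The count is of table rows, not events, and it depends on which rows are included: adding two graded endocrine rows and three confirmed rows for other irAEs gives 6/19 = 32%. No expected frequency by row is given. A reader might also infer that every missed event costs 17 points. Step 4 shows that this needs a cohort of 6 and a subject with no other flagged irAE.

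**Conclusion.** The point holds in a limited form. As SAP 18.2 is written, an irAE that is managed without corticosteroids, immunosuppressants or hormones and resolves without escalation cannot appear in the irAE rows of SAP 15.2.1 and 15.2.5. Grade 2 diarrhea/colitis is the clearest case and Grade 1 diarrhea/colitis the next. Grade 1 to 2 liver, Grade 1 creatinine and Grade 1 pneumonitis findings belong here only when they are reported as AEs.

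The direction is certain: any such loss lowers the reported incidence. Its size is unknown. The conclusion assumes that the preferred-term list covers the Table 6-2 event types and that sites answer the criterion 3 question literally. The DLT and PK primary endpoints are untouched, and nothing here bears on how irAEs are treated.

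**What to change.** In SAP 18.2, 15.2.1 and 15.2.5:

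1. Keep the four-criterion definition, and label its rows *irAEs treated with corticosteroids, immunosuppressants or hormones*. State how a missing answer to criterion 3 is handled.
2. Add, by cohort, a row *irAEs irrespective of treatment* that uses criteria 1, 2 and 4 without criterion 3. Criterion 4 should stay. Without it, an event with a clear other cause, such as infection, could count as immune-related.
3. Confirm whether the irAE eCRF page is completed when criterion 3 is No; the documents do not say. If it is not, applying the present rule for a missing 4a answer would count every such AE that meets criteria 1 and 2. In that case use criteria 1 and 2 plus relationship = related, and say so in the row label. Withholding of avelumab is not a good substitute: Protocol 5.1.3.1 withholds the infusion for any ongoing Grade 2 adverse drug reaction, immune-related or not.

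The cost is SAP wording and a few extra table rows from AE data already collected. The downside is that the added row is less specific and will show a higher irAE rate.

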**Table 6-1 Management of Hypersensitivity and Infusion-related Reactions Caused by Avelumab**

NCI-CTCAE Grade	Treatment Modification for Avelumab
Grade 1: Mild Mild transient reaction; infusion interruption not indicated; intervention not indicated	
 
Decrease avelumab infusion rate by 50% and monitor closely for any worsening.
 

Grade 2: Moderate Therapy or infusion interruption indicated but responds promptly to symptomatic treatment (eg, antihistamines, nonsteroidal antiinflammatory drug, narcotics, intravenous fluids); prophylactic medications indicated for ≤ 24 hours	
 
Temporarily discontinue avelumab infusion
 
Resume infusion at 50% of previous rate once infusion-related reaction has resolved or decreased to at least Grade 1 in severity and monitor closely for any worsening.
 

Grade 3 or Grade 4: Severe or Life-threatening Grade 3: Prolonged (eg, not rapidly responsive to symptomatic medication and/or brief interruption of infusion); recurrence of symptoms following initial improvement; hospitalization indicated for clinical sequelae Grade 4: Life-threatening consequences; urgent intervention indicated	
 
Stop the avelumab infusion immediately and disconnect infusion tubing from the subject
 
Subjects have to be withdrawn immediately from avelumab treatment and must not receive any further avelumab treatment.
 

NCI-CTCAE: National Cancer Institute-Common Terminology Criteria for Adverse Events.

Once the avelumab infusion rate has been decreased by 50% or interrupted due to an infusion-related reaction, it must remain decreased for the next scheduled infusion. If no infusion-related reaction is observed in the next scheduled infusion the infusion rate may be returned to baseline at the all subsequent infusions. If an infusion reaction occurs, all details about drug preparation and infusion must be recorded.

Subjects should be instructed to report any delayed reactions to the Investigator immediately.

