### Dose-limiting Toxicity

A DLT is defined as a  $\geq$  Grade 3 ADR according to the NCI-CTCAE v4.03, occurring during the DLT observation period of the dose escalation cohorts. An ADR is defined in this study as any AE suspected to be related to avelumab by the Investigator and/or Sponsor. A DLT must be confirmed by the SMC as being related to avelumab.

A DLT is specifically defined as any Grade  $\geq$  3 toxicity that is possibly, probably, or definitely related to avelumab, occurring during the DLT observation period, except for any of the following:

- Grade 3 infusion-related reaction resolving within 6 hours and controlled with medical management.
- Transient ( $\leq$  6 hours) Grade 3 flu-like symptoms or fever, which is controlled with medical management.
- Transient ( $\leq$  24 hours) Grade 3 fatigue, local reactions, headache, nausea, emesis that resolves to  $\leq$  Grade 1.
- Grade 3 skin toxicity, or Grade 3 LFT (ALT, AST, or gamma-glutamyl transferase) increase that resolves to  $\leq$  Grade 1 in less than 7 days after medical management (eg, immunosuppressant treatment) has been initiated.
- Grade 3 diarrhea unless to be discontinued according to Treatment Guidelines. In this case it would be an DLT again.
- Single laboratory values out of normal range that are unlikely to be related to avelumab according to the Investigator, do not have any clinical correlate, and resolve to  $\leq$  Grade 1 within 7 days with adequate medical management.
- Tumor flare phenomenon defined as local pain, irritation, or rash localized at sites of known or suspected tumor.

The ADRs (including DLTs) that require permanent discontinuation of avelumab are described in Section 5.1.3.1.

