- **Adverse Events Leading to Death:** adverse event leading to death (as recorded on the AE eCRF page, Outcome = Fatal, as well as AEs of Grade 5).
- **Related AE Leading to Death**
- **Immune Related Adverse Events (irAE):** immune related adverse events are identified via customized MedDRA PT queries and additionally classified by investigator according to case definition (two level approach). Details are included in Appendix 18.2.
- **Infusion Related Reactions (IRR):** IRRs are identified based on a list of MedDRA PTs. The detailed criteria of the timing relationship to infusion are specified in Appendix 18.2.

Incomplete AE-related dates will be handled as follows:

- Incomplete or missing start date:
 - In case the onset date is completely missing or the onset is in the same year (if the onset year is available only) or the onset is in the same month and year (if the day is missing) as start of study treatment, then the onset date will be replaced by the minimum of start of study treatment date and AE resolution date (imputed, if incomplete).
 - In all other cases the missing onset day or onset month will be replaced by 01.
- Incomplete or missing stop date:

- Incomplete stop dates will be replaced by the last day of the month (if day is missing only), if not resulting in a date later than the date of subject's death. In the latter case the date of death will be used to impute the incomplete stop date.
- In all other cases, the incomplete stop date will not be imputed.

AEs will be coded using the latest version of Medical Dictionary for Regulatory Activities (MedDRA). The severity of AEs will be graded by the investigator using the NCI-CTCAE version 4.03.

The AE reporting period for safety surveillance begins when the subject is included in the study (date of first signature of informed consent) and continues for all SAEs and treatment-related non-serious AEs through to the study's Safety Follow-up Phone Call, defined as 90 days (\pm 7 days) after the last administration of avelumab. Any SAE suspected to be related to avelumab must be reported whenever it occurs, irrespective of the time elapsed since the last administration of avelumab.

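### The 2-day resolution condition in SAP 18.2 can drop long, ongoing, partly dated or fatal symptom-coded infusion reactions from the infusion-related reaction tables

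*SAP*

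**What the plan says.** SAP 15.2 states that "IRRs are identified based on a list of MedDRA PTs" and refers to Appendix 18.2 for the timing criteria. The appendix gives two routes:

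- **Reaction terms.** Infusion related reaction, drug hypersensitivity, anaphylactic reaction, hypersensitivity and type 1 hypersensitivity count when onset is on the day of infusion "or the day after the study drug infusion (irrespective of resolution date").
- **Sign and symptom terms.** Pyrexia, chills, flushing, hypotension, dyspnoea, wheezing, back pain, abdominal pain and urticaria count only when they occur on the infusion day and are "resolved with end date within 2 days after onset".

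SAP 15.2.5 then tabulates IRRs by cohort, with rows for serious events, Grade ≥3, Grade ≥4, discontinuation and death ("Any IRRs leading to death"), each also for related events. SAP 15.2 replaces an AE stop date that lacks only the day by the last day of the month, or by the date of death if that is earlier. Other incomplete stop dates are left as they are.

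Protocol Table 6-1 gives three alternatives for a Grade 3 reaction: "Prolonged (eg, not rapidly responsive to symptomatic medication and/or brief interruption of infusion"), recurrence of symptoms after initial improvement, or "hospitalization indicated for clinical sequelae". Grade 4 is "Life-threatening consequences; urgent intervention indicated".

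**The concern.** A case definition for an acute reaction would normally rest on what is known at onset: the term, the timing and the suspected cause. The symptom route adds a condition on how the event ends. Among symptom-coded events, the ones that last longest are the least likely to be counted. Yet the rows that matter most in SAP 15.2.5 (serious, Grade ≥3, discontinuation, death) are where a long or unresolved course is most plausible.

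Infusion-related reactions are one of the two primary known risks named in Protocol 3.4, and an adverse event of special interest in Protocol 7.4.1.1. A reader will take the IRR tables as the summary of that risk in Chinese subjects. A zero in a severe row should not be the product of a date rule.

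**Working it through.** The SAP gives no figure to reproduce, so the check applies the SAP 18.2 rule case by case. All symptom cases start on the infusion day.

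| How recorded | Course | In the IRR tables? |
|---|---|---|
| Any of the five reaction terms | Any grade, any duration, fatal or not | Yes |
| Symptom term, Grade 3 or 4 | Ends within 2 days | Yes |
| Symptom term, any grade | Ends more than 2 days after onset | No |
| Symptom term, any grade | Ongoing, no end date | No: there is no end date to test |
| Symptom term, any grade | Onset on the 10th, end known only to the same month | No: imputed to the 28th to 31st, that is 18 to 21 days after onset, even if it truly ended the same day |
| Symptom term, any grade | End date missing or lacking the month | No: not imputed |
| Symptom term, fatal | Death more than 2 days after onset | No |
| Symptom term, fatal | Death within 2 days of onset | Unclear: no if *resolved* is read literally; yes if only the end date is tested and it equals the date of death |

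The partly dated row assumes that the SAP 15.2 imputation feeds the SAP 18.2 test. SAP 18.2 does not say otherwise.

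**Route back in.** There is none for IRRs. For immune-related events, the same appendix uses investigator answers on the eCRF and counts the event when the etiology answer is missing. The IRR rule uses only terms and dates, and an incomplete date works against inclusion.

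**Which rows are exposed.** A subject with short-lived chills and a 4-day Grade 3 hypotension after the same infusion still counts under any IRR, through the chills, but not under Grade ≥3. The severity rows are therefore more exposed than the overall row.

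**Size of one dropped event.** Take, as an illustration, a Grade 3 hypotension that starts on the infusion day and ends 4 days later.

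- Cohort of 6 (Protocol 5.1.1.1): 1/6 = 16.7% becomes 0/6 = 0%.
- All subjects (Protocol synopsis, about 21 and up to about 24): 1/21 = 4.8% or 1/24 = 4.2% becomes 0%.

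**How often.** The documents do not allow an estimate. The only severe rate given is in Protocol 3.4: Grade 4 infusion reactions in 3 of 1300 subjects. In 24 subjects that is 24 × 3/1300 = 0.055 expected. No Grade 3 rate is given, nor the share of reactions recorded by symptom.

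**The case against.** A reader might infer that severe and fatal IRRs as a class are removed, because the protocol defines Grade 3 as prolonged and the SAP demands short duration. The documents do not support that reading.

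- *Prolonged* in Table 6-1 is measured against prompt response to medication or brief interruption, not against 2 days. It is one of three alternatives, and Grade 4 has no duration element. The DLT definition itself describes a "Grade 3 infusion-related reaction resolving within 6 hours and controlled with medical management".
- A severe or fatal event coded to a reaction term is counted irrespective of resolution date.
- Table 6-1 grades the diagnosis of an infusion reaction. Protocol 7.4.1.1 points to event-specific CTCAE grades, so an event recorded as hypotension would be graded as hypotension.

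A reader might also infer that the death row is zero by construction for the nine symptoms. That rests on a literal reading of *resolved*. SAP 15.2 can set a stop date to the date of death, so a death within 2 days of onset could meet a date-only test. This is an ambiguity, not a certain exclusion.

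Three further points carry weight. Dropped events are not hidden: they stay in the general TEAE, serious and discontinuation outputs, and the death listing shows the day relative to the most recent infusion. DLTs are captured from the adverse event form (SAP 15.1), so no escalation decision depends on the IRR flag. And the 2-day limit buys specificity: in advanced cancer, same-day dyspnoea or pain that never resolves may be due to the disease. Loosening the main definition is therefore debatable.

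Whether sites are told to record the diagnosis rather than symptoms cannot be judged. Protocol 7.4.1.2 refers to separate eCRF conventions that are not part of these documents.

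None of this removes the core point. The stated rule still drops long, ongoing and partly dated symptom-coded reactions from the tables meant to describe this risk.

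**Conclusion.** The point holds for one defined group: the nine sign and symptom terms when the event lasts more than 2 days, is ongoing, has an incomplete end date or, on a literal reading, is fatal. The SAP 15.2.5 rows for Grade ≥3, serious, discontinuation and death can then be too low. Relative to the same definition without the condition, the error goes only one way, because the condition can only remove events. One event changes a cohort of 6 from 1/6 to 0/6.

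This assumes that some true reactions are recorded under symptom terms, and that a dropped event is a true infusion reaction rather than disease. The likelihood is unknown and may be small. The main definition can stay, so this is a cheap improvement rather than a flaw that undermines the safety analysis.

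**What to change.** 1. Keep the SAP 18.2 definition as the main line of the IRR tables.
2. Add one supportive line to the SAP 15.2.5 tables. It counts any of the nine symptom terms with onset on the infusion day, assessed as related to avelumab, and Grade ≥3, serious, fatal or leading to discontinuation, irrespective of end date. Take *related* from the bulleted definition in SAP 15.2 (related, or relationship not answered), because the sentence on related events in SAP 15.2.1 also names unrelated ones.
3. State that a missing, ongoing or imputed end date does not by itself exclude an event from the supportive line.
4. State how a fatal outcome is treated under the 2-day rule in the main line, including whether an end date equal to the date of death satisfies it.

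The cost is a few sentences in SAP 18.2 and one table line, from data already collected. The downside is that a few disease-related same-day symptoms may enter the supportive line. The relatedness requirement limits this, and the main line stays unchanged beside it.
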